10. SAMPLE SIZE

The sample size estimate outlined below is based on primary endpoint assessment only for the PerQseal® closure device.

The primary endpoint of safety will be assessed by comparison of the proportion of PerQseal® closure device closures with device related major vascular access site complications up to 1 months (P_{safety}) against a performance goal for safety (PG_{safety}) estimated from literature to be 12.5%.

The minimum sample size to demonstrate non-inferiority of safety against the literature based non-inferiority limit of 0.17 (refer to: Section 11.6 Primary Endpoint Analysis) with a one-sided significance level of 0.025 and study power of 90% is estimated to be 68 closures (assuming a 5% major vascular access site complication rate for the PerQseal® closure device). Refer to the independent statistical report for safety sample size in the CIP Appendix F: Independent Statistical Sample Size Report for Safety for details.

A one sided confidence interval is appropriate as the study is only interested in the upper bound of the major complication rate. Each complication will be analysed as a separate event.

Completion of 75 patients is recommended, this number of patients should be sufficient to demonstrate non-inferiority whilst allowing for approximately 10% dropout rate.

For Performance, in order to claim non-inferiority against technical success rate for 'perclose' or 'preclose' technique the lower bound or a (95%) confidence interval for PerQseal® technical success rate must be shown to be greater than the performance non inferiority limit. In order to achieve this, a minimum sample size of 44 closures is required to demonstrate non-inferiority in a single sample fixed one-sided significance level of 0.025 and power of 0.90 level. The secondary performance endpoint therefore does not drive sample size. The total planned sample size remains at 75 treated subjects.

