11.3 Statistical methods

For continuous variables, the mean, median, standard deviation, interquartile range and minimum-maximum value will be presented. In order to compare subgroups, the differences in means of the subgroups will be tested with a two-sample t-test (in case of 2 subgroups) or with one-way ANOVA (in case of >2 subgroups) in case the assumptions for the required tests are valid. If these assumptions are violated, testing will be done using independent samples Mann-Whitney U tests or Kruskal-Wallis tests (instead of one-way ANOVA).

For categorical variables counts and percentages will be presented. In order to compare differences between subgroups, categorical variables with an expected cell count of at least 5 in 80% of the cells (but no zero expected cell counts) will be tested using the Pearson chi-square test. For categorical variables that do not have an expected cell count of at least 5 in 80% of the cells (or that do have at least one zero expected cell count) and require the differences between the two treatment groups to be tested, the following will be done: Fisher's exact test will be performed for 2x2 contingency tables or the likelihood ratio test will be performed for larger contingency tables.

The tests for all subgroup comparisons assume a significance level of 0.05. No adjustment for multiple testing will be done for any of these variables, as these do not consider the primary endpoint.

Specification for the test concerning the primary endpoint can be found in Section 11.6.

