11.5 Variables

The study variables identified for comparisons/summaries are:

Primary Variables:

- i. Major device related vascular access site complication rate.
- ii. Serious Adverse Device Effect (SADE), Unanticipated Serious Adverse Device Effect (USADE) rate, as defined in the 'Clinical Investigation Definitions' (which is maintained in the Site File for each site).

Secondary Variables

- i. Safety: minor vascular access site complications related to the closure.
- ii. Adverse Device Effect (ADE), Serious Adverse Event (SAE) or Adverse Event (AE) rate, as defined in the 'Clinical Investigation Definitions'.

Performance: assessed by technical success rate for the PerQseal® closure device.

The potential influencing variables identified include:

- i. Patient age, gender, weight or Body Mass Index (BMI)
- ii. ACT
- iii. Co-existent diseases
- iv. Sheath size used
- v. Common Femoral Artery (CFA) diameter
- vi. Procedure to be performed

11.6 **Primary endpoint analysis**

The Safety of the PerQseal® closure device will be assessed by comparison of the proportion of PerQseal® closure device subjects with device related major vascular access site complication up to 1 months (P_{safety}) against a performance goal for safety (PG_{safety}). (The performance goal for safety for this study will be based on historical data extracted from literature for cut-down and suture closure.)

This will be achieved by testing for non-inferiority against a safety non-inferiority limit (N_{LS}), which is the predetermined PG_{safety} plus a non-inferiority margin delta. In order to claim non-inferiority against a safety driven PG_{safety} the upper bound of a one-sided (95%) confidence interval for the proportion of subjects with complications " P_{safety} " (using the exact method for estimating a Binomial proportion) must be shown to be less than the non-inferiority limit.

The PG_{safety} and non-inferiority margin delta have been derived from a Meta-analysis of major vascular access site complication rates for cut-down and suture closure from equivalent patient populations and sheath sizes of 12 - 24 F reported in the literature:

The proportion of complications is estimated to be 0.125 with a 95% Confidence Interval of 0.09 to 0.17. Given that the upper bound is 0.17 this justifies the use of 0.13 as valid PG_{safety} plus a non-inferiority margin of 0.04 yielding an overall non-inferiority limit (N_{LS}) of 0.17 for Safety.

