The test for non-inferiority for safety will be based on a one-sided test (at the 0.025 significance level) for a binomial proportion with hypotheses:

 H_{0S} : $P_{safety} \ge N_{LS}$ versus H_{1S} : $P_{safety} < N_{LS}$

Where: P_{safety} is the actual proportion of subjects with device related major vascular access site complications within the analysis population (ITT and PP).

And: N_{LS} is the non-inferiority limit for proportion of expected major vascular access site complications associated with cut-down and suture closure.

Non-inferiority analysis will be done by using the study data to calculate a confidence interval for the population proportion with major vascular access site complications directly related to the device. Demonstrating non-inferiority for safety necessitates rejecting the null hypothesis (H_{0S}) in favour of the alternative hypothesis (H_{1S}), in this case based on the upper limit of a 95% confidence interval for a population proportion being less than the non-inferiority limit.

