11.7 Secondary endpoints

Two secondary endpoints will be summarised for the entire group of subjects/closures:

-Minor device related vascular access site complications per subject up to 1 months (safety endpoint)

-Technical success rate for the PerQseal® closure device at discharge per closure is no worse than the technical success rates associated with the 'perclose' or 'preclose' technique following EVAR or TAVR.

The criteria for successful performance of the investigational device have been aligned with what is reported within the literature, ensuring a like for like comparison. A literature based performance control is the only effective source of data available for this study, as it is not applicable to compare the performance of a device with that of a surgical technique of cut-down and sutured closure, used for the safety control. Therefore, the performance of the PerQseal® (i.e. the proportion of successful closures) will be assessed by comparison of the proportion of PerQseal® closures which achieve acute haemostasis at the arteriotomy site and do not lead to alternative treatment (other than manual compression or adjunctive endovascular ballooning) (Pperformance) from the mITT group against a performance goal for performance (PGperformance). This will be achieved by testing for non-inferiority against a performance non-inferiority limit (NLP), which is the predetermined PGperformance minus a non-inferiority margin delta. In order to claim non-inferiority against a performance driven PGperformance the lower bound of a (95%) confidence interval for the proportion of successful "Pperformance" (using the exact method for estimating a Binomial proportion) must be shown to be greater than the non-inferiority limit.

The PG_{performance} and non-inferiority margin delta have been derived from a Meta-analysis of performance rates for percutaneous device closure (Prostar® XL and Perclose ProGlide®) from comparable patient populations reported in the literature.

The proportion with successful closure is estimated to be 0.84 with a 95% Confidence Interval of 0.81 to 0.87. Given that the lower bound is 0.81 this justifies the use of 0.84 as valid $PG_{performance}$ minus a non-inferiority margin of 0.03 yielding an overall non-inferiority limit (N_{LP}) of 0.81 for performance.

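### Technical success has its own formal non-inferiority claim with no testing order, so it can be claimed after the only primary hypothesis has failed

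*SAP*

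**What the plan says.** **Safety (primary).** SAP 11.6 gives a claim rule that begins "In order to claim non-inferiority against a safety driven" performance goal. It sets a limit of 0.17, states null and alternative hypotheses (H0S, H1S), and describes the test as "based on a one-sided test (at the 0.025 significance level) for a binomial proportion". The same section also states the rule through "the upper bound of a one-sided (95%) confidence interval for the proportion of subjects with complications", which is a 0.05 level. SAP 10 uses one-sided 0.025.

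**Technical success (secondary).** SAP 11.7 derives a goal of 0.84, a margin of 0.03 and a limit of 0.81. It then says "In order to claim non-inferiority against a performance driven PGperformance the lower bound of a (95%) confidence interval" for the success proportion "must be shown to be greater than the non-inferiority limit". SAP 10 repeats the intention ("For Performance, in order to claim non-inferiority against technical success rate") and gives the test a "single sample fixed one-sided significance level of 0.025 and power of 0.90 level", needing 44 closures.

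**Order of testing.** None is stated. SAP 10 notes that performance does not drive the sample size. The only sentence on multiplicity, in SAP 11.3, follows the subgroup comparisons: "No adjustment for multiple testing will be done for any of these variables, as these do not consider the primary endpoint".

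**The concern.** Technical success is labelled secondary but has everything a confirmatory test needs: a goal, a margin, a limit, an error level, a sample size and a rule for making the claim. That rule looks only at the performance bound. Nothing makes it depend on the safety result.

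Two things follow. The error rate across the two claims is not held at the 2.5% used for each. And the report could carry a formal non-inferiority statement on performance beside a failed primary safety test, with no rule agreed in advance on how to read that pair of results.

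**Working it through.** **The plan's own sample sizes.**
- Safety: p0 = 0.17, p1 = 0.05, one-sided 0.025, power 0.90 (SAP 10). The arcsine formula ((1.960 + 1.282) / (2·asin√0.17 − 2·asin√0.05))² gives 66.02, so 67, within one of the stated 68. The exact test at 68 has power 87.6%. That is a separate matter and does not affect this point.
- Performance: SAP 10 does not give the assumed success rate behind 44 closures. An exact test against 0.81 at one-sided 0.025 reaches 90.2% power at 44 closures if the true rate is 0.96. I use 0.96 below as an assumption only.

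**Nominal error over the two claims, both nulls true at their limits.**
- Upper bound: 0.025 + 0.025 = 0.05. If independent: 1 − 0.975² = 0.0494.
- With the one-sided 95% rule for the primary: 0.05 + 0.025 = 0.075. If independent: 1 − 0.95 × 0.975 = 0.0738.

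**Exact sizes.** Safety with 75 subjects passes at 6 events or fewer (97.5% upper bound 0.166), with size P(X ≤ 6 | 75, 0.17) = 2.04%. Performance counts limbs separately (SAP 9.3), so closures may exceed 75. I read its 95% interval as two-sided, to match the 0.025 in SAP 10.

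| Closures | Passes at | Size at 0.81 | At least one false claim, independent | Upper bound, any dependence |
|---|---|---|---|---|
| 75 | ≥ 68 | 1.75% | 1 − 0.9796 × 0.9825 = 3.8% | 2.04 + 1.75 = 3.8% |
| 80 | ≥ 72 | 2.21% | 1 − 0.9796 × 0.9779 = 4.2% | 2.04 + 2.21 = 4.3% |
| 85 | ≥ 77 | 1.23% | 1 − 0.9796 × 0.9877 = 3.2% | 2.04 + 1.23 = 3.3% |

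Positive correlation lowers these figures, but not below the larger single size (2.04% to 2.21%).

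**A concrete discordant result.** With 8/75 major complications the upper bound is 0.199 (97.5%) or 0.184 (95%), so safety fails under either reading. With 68/75 technical successes the lower bound is 0.817, above 0.81, so performance may be claimed.

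**How often safety fails (one-sided 0.025).** At a true rate of 5%: 8.1% with 75 evaluable, and 12.4% with 68 (75 × 0.9 = 67.5). At a true 8% with 75 evaluable: 39%.

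**How often performance passes (75 closures).** Power is 0.52, 0.75, 0.92 and 0.99 at true success rates of 0.90, 0.92, 0.94 and 0.96.

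**The conflict inside SAP 11.6.** At 7/75 events the 97.5% bound is 0.183 (fail) and the 95% bound is 0.168 (pass). The 95% rule has size 4.6%. A gate that depends on passing safety is therefore undefined at 7 events until the level is settled.

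**The case against.** **The two claims are distinct.** Safety is set against surgical cut-down and performance against percutaneous suture devices, and SAP 11.7 explains why. There is one primary endpoint and the sample size rests on it. Each claim is held at its own level, and the documents promise no study-wide 2.5%. This stands in part: how widely to draw the error family is partly convention. It does not supply a testing order, and the secondary label is not one.

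**Secondary endpoints are only summarised.** SAP 11.7 opens that way, and the shell of Table 4 shows only a percentage and counts. But the same section then sets a claim rule, and the primary endpoint's shell (Table 2) is just as bare.

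**The full protocol may hold the rule.** Only a synopsis is available, so this cannot be excluded.

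**Stronger readings that the documents do not support.**
- A reader might infer that the primary test's type I error is inflated. It is not, because the second test does not alter the first.
- A reader might infer that the study succeeds if either test passes. No section says so or lets performance rescue safety.
- A reader might take the 8.1%, 12.4% and 39% as false-claim rates. They are type II failures: 5% and 8% both lie below 0.17, so safety fails although the device meets the limit. A performance claim made alongside is correct if true success exceeds 0.81.

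**Conclusion.** The point holds as a gap in the claim rules. Two free-standing non-inferiority claims are planned and nothing prevents the secondary from being claimed after the primary has failed. The excess error is modest: at most 5% nominally against 2.5% per test, and about 3.2% to 4.2% with exact tests. The exact figures assume both nulls true at 0.17 and 0.81, 75 subjects for safety, 75 to 85 closures for performance, independence, and a primary level of 0.025. Under the one-sided 95% wording the nominal bound is 7.5%.

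The larger practical matter is how a discordant result would be read, since it can arise readily whenever safety fails and true technical success is high. The primary conclusion itself is not at risk, so this is a worthwhile low-cost improvement and not a flaw in the main result.

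**What to change.** 1. Reconcile the primary level first. In SAP 11.6, replace the one-sided 95% bound with a one-sided 97.5% exact upper bound, to match the 0.025 level there and in SAP 10.
2. Then add to SAP 11.7: technical success is tested for a non-inferiority claim at one-sided 0.025 only if H0S is rejected in the ITT population; otherwise its rate and exact interval are reported with no claim. ITT has to be named because SAP 11.6 lists both ITT and PP. SAP 11.1 already makes PP the secondary population for this endpoint.

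Both tests keep the full 0.025. Family-wise error is at most 0.025: when the safety null is true, any false claim requires first rejecting it, and when only the performance null is true, a false claim requires rejecting that one.

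**Cost.** Wording only, with no added patients. The sponsor gives up any formal performance claim when safety fails, including claims that would have been correct. At a true 5% complication rate that is 8.1% of the time with 75 evaluable and 12.4% with 68. At a true 8% with 75 evaluable it is 39%.

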11.8 Other safety assessments

Based on the CRF data, cumulative adverse event / complication rates for all time points will be presented for all subjects combined. This will also be done for serious adverse events / complications and for deaths.

A summary for all subjects combined will be presented for the Serious Adverse Event (SAE) rates, the rates of Serious Adverse Device Effects (SADEs)/ Unanticipated Serious Adverse Device Effects (USADEs), the rates of procedure related SAEs and the rates of minor/major vascular access site complications at the end of the study. Additionally, cumulative rates for all time points will be presented for SAEs, major device related vascular access site complications and minor device related vascular access site complications.

11.9 Other performance assessments

Time from insertion of the PerQseal[®] closure device into the introducer sheath to departure from theatre, device deployment time and time to haemostasis will be summarised for the entire group of subjects in the study

11.10 Missing data

Historically (which includes 120 subjects and 136 closures across all Frontier studies) there have not been any device related access site complications beyond patient discharge from hospital. So it is expected that all safety data will be captured for all enrolled subjects. All subjects with available data will be used in the statistical analyses. All implanted subjects will be assessed for technical success. With regard to assessment of device related complications through 1 months, data on all subjects through the point of last follow up prior to or at 1 months will be included in the analysis. For the primary analysis, no imputation is expected to be performed for missing data. However, in the unlikely event that there is missing critical safety data Bayesian models may be utilised for sensitivity to investigate the impact of incomplete follow-up.

11.11 Protocol Deviations

All protocol deviations will be summarised and listed in detail in the Clinical Study Report. Protocol deviations will be categorised as follows: deviations that occurred with respect to baseline inclusion/exclusion criteria, follow-up visits or assessment not completed, visit or assessment not completed per study protocol, or visit or assessment out of window. All the protocol deviations will be assessed for their potential influence on the safety and/or performance results of the study.

11.12 Changes to the analysis specified in the protocol

There are no planned additional analysis other that what has been outlined within the Protocol and SAP. In the event that any additional or ad-hoc analysis is performed not already listed within the SAP or protocol, this will be clearly indicated within the Clinical Study Report.

12. DATA MANAGEMENT

All data management will be documented in a seperate Data Management Plan.

13. OVERVIEW OF TABLES TO BE GENERATED

Table 1. Enrollment summary	. 25
Table 2. Primary endpoint	. 25
Table 3. Primary endpoint subgroup comparisons	. 25
Table 4. Secondary endpoints	. 29
Confidential & proprietary information, not to be reproduced or made available to third parties with	thout

T. I. O. D II	~ .
Table 6. Baseline demographics and medical history	
Table 7. Baseline physical examination	
Table 8. Baseline characteristics subgroup comparisons	
Table 9. Baseline laboratory tests	43
Table 10. Baseline CT angiogram / angiogram of femoral vasculature	43
Table 11. Procedural information	44
Table 12. Angiogram of ipsilateral femoral vasculature	45
Table 13. Device and deployment details	47
Table 14. Post-procedural angiogram of femoral vasculature	48
Table 15. Pre-discharge examination	49
Table 16. Groin condition	50
Table 17. ABI	51
Table 18. Lower extremity pulses (palpate)	52
Table 19. 3 Month Duplex ultrasonography	53
Table 20. Follow-up examination of the puncture site	55
Table 21. Medication	55
Table 22. Adverse events / complications summary (CRF data)	56
Table 23. Protocol deviations summary	57
Table 24. Summary of major vascular access site complication types up to 1 mont	ths
58	
Table 25. Summary of minor vascular access site complication types up to 3 mont	ths
59	
14. OVERVIEW OF LISTS TO BE GENERATED	
List 1. List of all centres that have enrolled subjects (colour coded by country)	60
List 2. Discontinued subjects	60
List 3. Protocol deviations	60
List 4. Non-serious adverse events	61
List 5. Serious adverse events	61
List 6. CEC adjudications	61
List 7. Demographics	62
Confidential & proprietary information, not to be reproduced or made available to third parties with prior consent from Vivasure Medical Ltd and not to be used in any unauthorised way.	out

15. OVERVIEW OF FIGURES TO BE GENERATED

16. TABLES, LISTS AND FIGURES SHELLS

This section will give the format and structure of all tables, lists and figures to be produced in the final Clinical Study Report (CSR).

These detailed specifications can undergo minor revisions during the production phase without needing to revise the SAP. Minor revisions are defined as revisions that do not invalidate any of the specifications in Section 11

16.1 **Tables to be generated**

Table 1. Enrollment summary

Centre	Procedure	No.	No. of	Males/Females	Mean	No. 1	No. 3
		Subjects	closures		Age	month	month
		Enrolled				FU	FU
F4-1	TAVI	XX	XX	xx/xx	XX.X	XX	XX
F4-1	EVAR	XX	XX	xx/xx	XX.X	xx	XX
F4-1	TEVAR	XX	XX	xx/xx	xx.x	XX	XX
F4-1	Other	XX	XX	xx/xx	xx.x	XX	XX

Table 2. Primary endpoint

	% (n/N)	
Major device related	xx.x (xx/xx)	
vascular access site		
complications up to 1		
months		

Table 3. Primary endpoint subgroup comparisons¹

% (n/N)	p-value
 	 

¹ This table will be omitted in the case of low major complication rates and a note will be made of this in the report.

Confidential & proprietary information, not to be reproduced or made available to third parties without prior consent from Vivasure Medical Ltd and not to be used in any unauthorised way.

Major device related

complications up to 1 months

 Centre 1
 xx.x (xx/xx)

 Centre 2
 xx.x (xx/xx)

. . .

Centre x xx.x (xx/xx) x.xxx

Major device related

complications up to 1 months

 TAVI
 xx.x (xx/xx)

 EVAR
 xx.x (xx/xx)

 TEVAR
 xx.x (xx/xx)

Other xx.x (xx/xx) x.xxx

Major device related

complications up to 1 months

Male gender xx.x (xx/xx)

Female gender xx.x (xx/xx) x.xxx

Major device related

complications up to 1 months

 $BMI \le 30 \text{ kg} \qquad \qquad xx.x (xx/xx)$

BMI > 30 kg xx.x(xx/xx) x.xxx

Major device related

complications up to 1 months

No hypertension xx.x (xx/xx)

Hypertension xx.x (xx/xx) x.xxx

Major device related

complications up to 1 months

No diabetes xx.x (xx/xx)

Diabetes xx.x (xx/xx) x.xxx

Major device related

complications up to 1 months

No severe acute non-cardiac xx.x (xx/xx)

systemic disease,

autoimmune disease or

terminal illness

Severe acute non-cardiac xx.x (xx/xx) x.xxx

systemic disease,

autoimmune disease or

terminal illness

Major device related

complications up to 1 months

No bleeding diatheses xx.x (xx/xx)

Bleeding diatheses xx.x (xx/xx) x.xxx

Major device related

complications up to 1 months

No peripheral vascular xx.x (xx/xx)

disease

Peripheral vascular disease xx.x (xx/xx) x.xxx

Major device related

complications up to 1 months

No previous peripheral xx.x (xx/xx)

vascular surgery involving the

aorta or lower extremities

Previous peripheral vascular xx.x (xx/xx) x.xxx

surgery involving the aorta or

lower extremities

Major device related

complications up to 1 months

No claudication xx.x (xx/xx)

Claudication xx.x (xx/xx) x.xxx

Major device related

complications up to 1 months

No previous arterial access xx.x (xx/xx)

procedure using proposed

artery

Previous arterial access procedure using proposed artery	xx.x (xx/xx)	x.xxx
Major device related complications up to 1 months		
Largest procedural sheath size used ≤ 18 F	xx.x (xx/xx)	
Largest procedural sheath size used > 18 F CFA size?	xx.x (xx/xx)	x.xxx
Age		
Age at procedure ≤ 77	xx.x (xx/xx)	
Age at procedure > 77	xx.x (xx/xx)	x.xxx
Major device related complications up to 1 months		
Sheath size to femoral artery diameter ratio ≤ 1.05	xx.x (xx/xx)	
Sheath size to femoral artery diameter ratio > 1.05	xx.x (xx/xx)	x.xxx
Major device related		
complications up to 1 months		
ACT level at surgery ≤ 160 s	xx.x (xx/xx)	
ACT level at surgery > 160 s	xx.x (xx/xx)	X.XXX

Table 4. Secondary endpoints

	% (n/N)
Minor device related vascular access site	xx.x (xx/xx)
complications up to 1 months	
Technical success rate	xx.x (xx/xx)

Table 5. Compliance to eligibility criteria

	% (n/N)
Patients with 100% compliance to eligibility criteria	xx.x (xx/xx)
Inclusion criteria	Yes: % (n/N)
Patient is over 18 years of age	xx.x (xx/xx)
Patient signed informed consent	xx.x (xx/xx)
Patient indicated for an endovascular procedure using a common femoral arteriotomy created by a 12 – 20 F sheath.	xx.x (xx/xx)
Exclusion criteria	No: % (n/N)
Severe acute non-cardiac systemic disease or terminal illness with a life	xx.x (xx/xx)
expectancy of less than six months	
Evidence of systemic bacterial or cutaneous infection, including groin infection	xx.x (xx/xx)
Known bleeding diathesis, definite or potential coagulopathy, platelet count $<$	xx.x (xx/xx)
$100,\!000/\!\mu I$ or patients on long term anticoagulants with an INR greater than 1.2	
at time of procedure or known type II heparin-induced thrombocytopenia	
Severe; claudication or peripheral vascular disease (e.g. Rutherford category ${\bf 3}$	xx.x (xx/xx)
or greater or ABI < 0.5), documented untreated iliac artery diameter stenosis $>$	
50% or previous bypass surgery/stent placement in the common femoral artery	
of ipsilateral limb.	
Known allergy to any of the materials used in the PerQseal $\! \! \! \! \! \! \! \! \! \! \! \! \! \! \! \! \! \! \!$	xx.x (xx/xx)
for Use)	
Subject has undergone a percutaneous procedure using a non-absorbable	xx.x (xx/xx)
vascular closure device (excluding suture mediated) for haemostasis in the	
ipsilateral target leg	
Patients that have undergone a percutaneous procedure in the ipsilateral leg,	xx.x (xx/xx)
within the previous 30 days	
Patients that have undergone a percutaneous procedure using an absorbable	xx.x (xx/xx)
intravascular closure device for haemostasis, in the ipsilateral leg, within the	
previous 90 days	

Evidence of arterial diameter stenosis > 20% or anterior or circumferential	xx.x (xx/xx)
calcification within 20 mm proximal or distal to target arteriotomy site based on	
pre-procedure CT angiography	
Females who are pregnant or lactating or in fertile period not taking adequate	xx.x (xx/xx)
contraceptives	
Patients that have a lower extremity amputation from the ipsilateral or contralateral limb Arterial access other than common femoral artery obtained for ipsilateral target	xx.x (xx/xx) xx.x (xx/xx)
leg	λι.λ (λυλλι)
Subject has a tissue tract expected to be greater than 10 cm	xx.x (xx/xx)
Use of thrombolytic agents within 24 hours prior to or during the endovascular	xx.x (xx/xx)
procedure which causes fibrinogen < 100 mg/dl	701.71 (700701)
Significant blood loss/transfusion (defined as requiring transfusion of 4 or more	xx.x (xx/xx)
units of blood products) during index procedure or within 30 days prior to index	(,
procedure	
Activated clotting time (ACT) > 350 seconds immediately prior to sheath removal	xx.x (xx/xx)
or if ACT measurements are expected to be > 350 seconds for more than 24	, ,
hours after index procedure	
Target puncture site is located in a vascular graft	xx.x (xx/xx)
Target arteriotomy in the profunda femoris or superficial femoral artery or is in	xx.x (xx/xx)
common femoral artery, but within 10 mm proximal of the bifurcation of the	
Superficial Femoral /Profunda Femoris artery	
PerQseal® Introducer-sheath to ipsilateral femoral artery diameter ratio is greater	xx.x (xx/xx)
than or equal to 1.05. (For S Introducer vessel lumen diameter of less than 6 mm.	
For L Introducer vessel lumen diameter of less than 7 mm.)	
Subjects with an acute haematoma of any size, arteriovenous fistula or	xx.x (xx/xx)
pseudoaneurysm at the target access site; or angiographic evidence of arterial	
laceration or dissection within the external iliac or femoral artery before the use	
of the PerQseal [®] closure device	

Table 6. Baseline demographics and medical history

	N	Mean	Median	Standard deviation	IQR		Min - Max
Age (years)	XX	XX.X	XX.X	XX.X	XX – XX		XX – XX
Height (cm)	XX	xxx.x	xxx.x	XX.X	XXX.X	_	XXX.X – XXX.X
					XXX.X		
Weight (kg)	XX	XXX.X	XXX.X	XX.X	XXX.X	_	XXX.X – XXX.X
					XXX.X		
	% (n/N)						
Hypertension	xx.x (xx/xx)						
Diabetes	xx.x (xx/xx)						
Severe acute non-	xx.x (xx/xx)						
cardiac systemic							
disease, autoimmune							
disease or terminal							
illness							
Clinically significant	xx.x (xx/xx)						
peripheral vascular							
disease							
Bleeding diatheses	xx.x (xx/xx)						
Previous peripheral	xx.x (xx/xx)						
vascular surgery							
involving the aorta or							
lower extremities							
Claudication	xx.x (xx/xx)						

Table 7. Baseline physical examination

	N(%)	Mean	Median	Standard	IQR	Min - Max
				deviation		
Age	XX	XXX.X	XXX.X	XX.X	xxx.x – xxx.x	XXX.X — XXX.X
Males	xx(xx.x)					
Females	xx(xx.x)					
Weight	XX	XXX.X	XXX.X	XX.X	xxx.x - xxx.x	xxx.x - xxx.x
Height	XX	XXX.X	XXX.X	XX.X	xxx.x - xxx.x	xxx.x - xxx.x
	% (n/N)					
Location of groin						
puncture to be used						
with Frontier Closure						
device						
Left leg	xx.x (xx/xx)					
Right leg	xx.x (xx/xx)					
Both legs	xx.x (xx/xx)					

FRONTIER IV - Statistical Analysis Plan

DOC-DP2-81 Rev 01

Table 8. Baseline characteristics subgroup comparisons

	N	Mean	Median	Standard	IQR	Min - Max	p-value
				deviation			
Age (years)							
Centre 1	XX	XX.X	xx.x	XX.X	xx.x - xxx.x	xx.x - xxx.x	
Centre 2	XX	XX.X	xx.x	XX.X	xx.x - xxx.x	xx.x - xxx.x	
Centre x	XX	XX.X	XX.X	XX.X	xx.x - xxx.x	xx.x - xxx.x	X.XXX
A (
Age (years)							
TAVI	xx	XX.X	XX.X	XX.X	XX.X - XXX.X	XX.X - XXX.X	
EVAR	XX	XX.X	XX.X	XX.X	XX.X - XXX.X	XX.X - XXX.X	
TEVAR	xx	XX.X	XX.X	XX.X	xx.x - xxx.x	XX.X - XXX.X	
Other	XX	XX.X	xx.x	XX.X	XX.X - XXX.X	xx.x - xxx.x	x.xxx
BMI (kg/m²)							
Centre 1	xx	xxx.x	xxx.x	XX.X	xxx.x – xxx.x	xxx.x – xxx.x	
Centre 2	XX	xxx.x	XXX.X	XX.X	xxx.x - xxx.x	xxx.x - xxx.x	
Centre x	XX	XXX.X	xxx.x	XX.X	xxx.x - xxx.x	XXX.X - XXX.X	X.XXX
BMI (kg/m²)							
TAVI	XX	xxx.x	XXX.X	XX.X	xxx.x – xxx.x	xxx.x – xxx.x	

FR	FRONTIER IV - Statistical Analysis Plan								
DC	C-DP2-81 Rev	01		V	iva sure				
ı	EVAR	XX	XXX.X	XXX.X	XX.X	xxx.x - xxx.x	xxx.x - xxx.x		
-	TEVAR	xx	XXX.X	XXX.X	XX.X	xxx.x - xxx.x	xxx.x - xxx.x		
(Other	XX	XXX.X	XXX.X	XX.X	XXX.X - XXX.X	XXX.X - XXX.X	X.XXX	
,	ACT (s)								
(Centre 1	XX	XX.X	XX.X	XX.X	xx.x - xx.x	XX.X - XX.X		
(Centre 2	XX	XX.X	XX.X	XX.X	XX.X - XX.X	xx.x - xx.x		
	 Centre x	xx	XX.X	xx.x	xx.x	xx.x – xx.x	xx.x – xx.x	X.XXX	
,	ACT (s)								
-	TAVI	XX	XX.X	XX.X	XX.X	xx.x - xx.x	xx.x - xx.x		
i	EVAR	xx	XX.X	XX.X	XX.X	xx.x - xx.x	XX.X - XX.X		
-	TEVAR	xx	XX.X	XX.X	XX.X	xx.x - xx.x	XX.X - XX.X		
(Other	XX	XXX.X	xxx.x	XX.X	XXX.X - XXX.X	XXX.X - XXX.X	x.xxx	
;	Sheath size (F)								
(Centre 1	XX	XX.X	XX.X	XX.X	xx.x - xx.x	xx.x - xx.x		
(Centre 2	XX	xx.x	xx.x	xx.x	xx.x - xx.x	xx.x - xx.x		
•									
(Centre x	XX	XX.X	XX.X	XX.X	XX.X - XX.X	xx.x - xx.x	X.XXX	

Sheath size (F)

RONTIER IV - Statistical Analysis Plan								
DOC-DP2-81	Rev 01			Viva				
TAVI	xx	XX.X	xx.x	xx.x	xx.x - xx.x	xx.x - xx.x		
EVAR	XX	XX.X	xx.x	XX.X	xx.x - xx.x	xx.x - xx.x		
TEVAR	XX	XX.X	XX.X	XX.X	xx.x - xx.x	xx.x - xx.x		
Other	XX	XXX.X	XXX.X	xx.x	XXX.X - XXX.X	XXX.X — XXX.X	X.XXX	
Sheath size to fe	emoral							
artery diameter r	atio							
Centre 1	xx	XX.X	XX.X	XX.X	xx.x - xx.x	xx.x - xx.x		
Centre 2	XX	XX.X	xx.x	XX.X	xx.x - xx.x	xx.x - xx.x		
Centre x	XX	XX.X	XX.X	xx.x	XX.X - XX.X	XX.X - XX.X	X.XXX	
Sheath size to fe	moral							
artery diameter r	atio							
TAVI	xx	XX.X	XX.X	XX.X	xx.x - xx.x	xx.x - xx.x		
EVAR	xx	XX.X	XX.X	XX.X	xx.x - xx.x	xx.x - xx.x		
TEVAR	xx	XX.X	xx.x	XX.X	xx.x - xx.x	xx.x - xx.x		
Other	xx	XXX.X	XXX.X	XX.X	xxx.x - xxx.x	xxx.x - xxx.x	X.XXX	
	% (n/N)	p-value						
With hypertension	n							
Centre 1	xx.x (xx/xx)							
Centre 2	xx.x (xx/xx)							
Centre x	xx.x (xx/xx)	X.XXX						

FRONTIER IV - Statistical Analysis Plan

DOC-DP2-81 Rev 01

Without hypertension

Centre 1 xx.x(xx/xx)Centre 2 xx.x(xx/xx)

Centre x xx.x(xx/xx)X.XXX

With hypertension

TAVI xx.x(xx/xx)**EVAR** xx.x(xx/xx)**TEVAR** xx.x(xx/xx)

Other xx.x(xx/xx)X.XXX

Without hypertension

TAVI xx.x(xx/xx)**EVAR** xx.x(xx/xx)**TEVAR**

xx.x (xx/xx)

xx.x(xx/xx)

X.XXX

With diabetes

Other

Centre 1 xx.x(xx/xx)Centre 2 xx.x(xx/xx)

xx.x(xx/xx)Centre x X.XXX

DOC-DP2-81 Rev 01

Without diabetes

Centre 1 xx.x (xx/xx)
Centre 2 xx.x (xx/xx)

• • •

Centre x xx.x (xx/xx) x.xxx

With diabetes

 TAVI
 xx.x (xx/xx)

 EVAR
 xx.x (xx/xx)

 TEVAR
 xx.x (xx/xx)

Other xx.x (xx/xx)

X.XXX

Without diabetes

TAVI xx.x (xx/xx) EVAR xx.x (xx/xx)

TEVAR xx.x (xx/xx)

Other xx.x (xx/xx) x.xxx

Male gender

Centre 1 xx.x (xx/xx)
Centre 2 xx.x (xx/xx)

...

Centre x xx.x (xx/xx) x.xxx

DOC-DP2-81 Rev 01

Female gender

Centre 1 xx.x (xx/xx)
Centre 2 xx.x (xx/xx)

• • •

Centre x xx.x (xx/xx) x.xxx

Male gender

 TAVI
 xx.x (xx/xx)

 EVAR
 xx.x (xx/xx)

 TEVAR
 xx.x (xx/xx)

Other xx.x (xx/xx) x.xxx

Female gender

 TAVI
 xx.x (xx/xx)

 EVAR
 xx.x (xx/xx)

 TEVAR
 xx.x (xx/xx)

Other xx.x (xx/xx) x.xxx

With severe acute non-cardiac systemic disease,

autoimmune disease or terminal illness

Centre 1 xx.x (xx/xx)
Centre 2 xx.x (xx/xx)

. . .

DOC-DP2-81 Rev 01

Centre x xx.x (xx/xx) x.xxx

Without severe acute non-cardiac systemic disease,

autoimmune disease or terminal illness

Centre 1 xx.x (xx/xx)
Centre 2 xx.x (xx/xx)

. . .

Centre x xx.x(xx/xx) x.xxx

With severe acute non-cardiac systemic disease,

autoimmune disease or terminal illness

 TAVI
 xx.x (xx/xx)

 EVAR
 xx.x (xx/xx)

 TEVAR
 xx.x (xx/xx)

Other xx.x (xx/xx) x.xxx

Without severe acute non-cardiac systemic disease,

autoimmune disease or terminal illness

 TAVI
 xx.x (xx/xx)

 EVAR
 xx.x (xx/xx)

 TEVAR
 xx.x (xx/xx)

Other xx.x(xx/xx) x.xxx

With bleeding diatheses

DOC-DP2-81 Rev 01

Centre 1 xx.x (xx/xx)

Centre 2 xx.x (xx/xx)

. . .

Centre x xx.x (xx/xx) x.xxx

Without bleeding diatheses

Centre 1 xx.x (xx/xx)

Centre 2 xx.x (xx/xx)

...

Centre x xx.x (xx/xx) x.xxx

With bleeding diatheses

TAVI xx.x (xx/xx)

EVAR xx.x (xx/xx)

TEVAR xx.x (xx/xx)

Other xx.x (xx/xx) x.xxx

Without bleeding diatheses

TAVI xx.x(xx/xx)

EVAR xx.x(xx/xx)

TEVAR xx.x(xx/xx)

Other xx.x (xx/xx) x.xxx

DOC-DP2-81 Rev 01

With clinically

significant peripheral

vascular disease

Centre 1 xx.x(xx/xx)

Centre 2 xx.x (xx/xx)

• • •

Centre x xx.x (xx/xx) x.xxx

Without clinically

significant peripheral

vascular disease

Centre 1 xx.x (xx/xx)

Centre 2 xx.x (xx/xx)

. . .

Centre x xx.x (xx/xx) x.xxx

With clinically

significant peripheral

vascular disease

TAVI xx.x (xx/xx)

EVAR xx.x (xx/xx)

TEVAR xx.x (xx/xx)

Other xx.x (xx/xx) x.xxx

DOC-DP2-81 Rev 01

Without clinically

significant peripheral

vascular disease

 TAVI
 xx.x (xx/xx)

 EVAR
 xx.x (xx/xx)

 TEVAR
 xx.x (xx/xx)

Other xx.x (xx/xx) x.xxx

Table 9. Baseline laboratory tests

	N	Mean	Median	Standard	IQR	Min - Max
				deviation		
Platelets (10³ cells/µl)	XX	XXX.X	XXX.X	XX.X	XXX.X — XXX.X	XXX.X — XXX.X
	% (n/N)					
Subjects on	xx.x (xx/xx)					
thrombolytic therapy						
	N	Mean	Median	Standard	IQR	Min - Max
				deviation		
If yes, fibrinogen	XX	XXX.X	XXX.X	XX.X	xxx.x – xxx.x	XXX.X — XXX.X
(mg/dl)						
	% (n/N)					
MRSA screening						
Positive	xx.x (xx/xx)					
Negative	xx.x (xx/xx)					

Table 10. Baseline CT angiogram / angiogram of femoral vasculature

	N	Mean	Median	Standard deviation	IQR	Min - Max
Common femoral	XX	XX.X	XX.X	X.X	XX.X — XX.X	xx.x – xx.x
artery lumen						
diameter (mm)						
	% (n/N)					
Evidence of	XX.X					
stenosis within	(xx/xx)					
20 mm of						
intended access						
site						
	N	Mean	Median	Standard	IQR	Min - Max
				deviation		

	N	Mean	Median	Standard deviation	IQR	Min - Max
If yes, estimate percentage	XX	XX.X	XX.X	X.X	XX.X — XXX.X	XX.X — XXX.X

DOC-DP2-81 Rev 01

Table 11. Procedural information

	% (n/N)					
Type of anaesthesia						
None	xx.x (xx/xx)					
Local	xx.x (xx/xx)					
Block	xx.x (xx/xx)					
General	xx.x (xx/xx)					
Patient sedated	xx.x (xx/xx)					
	N	Mean	Median	Standard	IQR	Min - Max
				deviation		
ACT (s)	XX	XX.X	XX.X	XX.X	xx.x – xx.x	XX.X — XX.X
Largest sheath size used (F)	xx	XX.X	XX.X	XX.X	xx.x - xx.x	XX.X - XX.X
	% (n/N)					
Anticoagulant/antiplatelet therapy given during procedure	xx.x (xx/xx)					
Significant blood loss/transfusion during procedure	xx.x (xx/xx)					
	N	Mean	Median	Standard	IQR	Min - Max
				deviation		
Approximate depth of tissue tract (mm)	XX	XX.X	XX.X	X.X	XX.X - XX.X	XX.X — XX.X
	% (n/N)					
Haematoma formation at ipsilateral access site	xx.x (xx/xx)					
If yes, Leg/s: estimated	xx.x (xx/xx)					
If yes, Leg/s: measured	xx.x (xx/xx)					

_	N	Mean	Median	Standard	IQR	Min - Max
				deviation		
If yes, size (mm²)	XX	XXXX.X	XXXX.X	XXX.X	xxxx.x – xxxx.x	xxxx.x – xxxx.x
	% (n/N)					
AV fistula at ipsilateral access site	xx.x (xx/xx)					
Pseudoaneurysm at ipsilateral access site	xx.x (xx/xx)					

Table 12. Angiogram of ipsilateral femoral vasculature

	% (n/N)
Arteriotomy puncture is	xx.x (xx/xx)
within the common	
femoral artery	
Arteriotomy in the	xx.x (xx/xx)
profunda femoris or	
superficial femoral	
artery or is in cfa, but	
within 10 mm proximal	
of the bifurcation of the	
Superficial Femoral	
/Profunda Femoris	
artery	
Perforation/dissection	xx.x (xx/xx)

Confidential & proprietary information, not to be reproduced or made available to third parties without prior consent from Vivasure Medical Ltd and not to be used in any unauthorised way. Page 45 of 64

DOC-DP2-81 Rev 01

Evidence of stenosis within 20 mm of access site within artery	xx.x (xx/xx)					
